## 9. Statistical Considerations

### 9.1 Study Objectives

Rev.10/15

The primary objective of this randomized, placebo-controlled, double-blinded, phase III study is to determine whether Exemestane + Entinostat (Arm A) improves progression-free survival (PFS) and/or overall survival (OS) compared to the Exemestane + Placebo (Arm B) in patients with hormone receptor-positive, human epidermal growth factor receptor 2 (HER2)-negative locally advanced or metastatic breast cancer (MBC) who have experienced disease progression after non-steroidal AI use in the adjuvant setting (within 12 months prior to enrollment) or in the metastatic setting.

Both PFS and OS are primary endpoints, and the study is designed to show an improvement in either PFS or OS. PFS is defined to be time from randomization to the earliest of documented disease progression as defined by the Response Evaluation Criteria In Solid Tumors (RECIST) 1.1 criteria, new primary breast cancer, or death without progression. Disease assessment will continue until disease progression, even after non-protocol anti-cancer therapy is started. Cases with incomplete follow up or without adequate disease evaluations will be censored at the date last documented to be free of progression, regardless of whether non-protocol anti-cancer therapy is started or not. Tumor response and progression will be defined by central review, including time point-by-time point radiologist reader review at the ACR Imaging Core Lab for patients with radiographically measurable/evaluable disease, and/or an independent review committee for patients with measurable/non-measurable disease that is not radiographically evident (i.e., skin lesions). OS is defined to be time from randomization to death from any cause, censoring cases who had not died at the date last known alive.

This study is aimed to give adequate power for both PFS and OS comparisons. The one-sided type I error of 0.025 is split between two hypotheses tests to control the overall type I error rate for the whole trial. Specifically, type I error rate is 0.001 for PFS test and 0.024 for OS test.

Rev.10/15

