#### Interim analysis for OS tests

Regardless of PFS results, the first interim analysis of OS will be performed at the final PFS analysis time (expected to be 24 months after study activation-see Section [9.2.1](#)). Interim analysis for OS will then be performed biannually until either the criteria for early stopping (described below) are met or the total planned number of OS events has been reported. Of note, interim analyses will be skipped if the change in the information since the previous interim analysis is less than 10%. In addition, when the information time reaches 90% or more, interim analysis will not be conducted, and the final analysis of OS will be performed when full information is reached. These interim analyses will be monitored by ECOG-ACRIN DSMC. Table 9.2 shows the operating characteristics for OS endpoint.

At each interim analysis, the stratified log rank test statistic will be computed. To preserve the overall one-sided type I error rate at 2.4% for the OS endpoint, critical values for rejecting null hypothesis at the interim analyses will be determined using a truncated version of the Lan-DeMets spending function corresponding to the O'Brien-Fleming boundary (1979). If the boundary is crossed at an interim analysis or at the final analysis, then the null hypothesis will be rejected, and the Exemestane + Entinostat therapy is superior to the exemestane monotherapy in terms of OS. If the criteria for rejecting the null hypothesis are not met, then it will be concluded that this trial fails to show superiority of Exemestane + Entinostat therapy over the exemestane monotherapy on OS.

Because interim analyses are timed to coincide with the ECOG-ACRIN DSMC meetings, these boundaries may change depending on the number of observed OS events at that time. Also, because of

delays in data submission and processing, it is likely that actual analysis times will be 6-12 months later.

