at diagnosis, prior adjuvant chemotherapy, prior hormonal therapy, et al. The assumption of proportionality in the Cox models will be assessed by investigating the weighted Schoenfeld residuals for each predictor. Patients with missing values for covariates will be excluded from modeling when the proportion of missingness is less than 5% and will be imputed appropriately if the proportion of missingness is  $\geq 5\%$ . ORR will be summarized along with the exact binomial 95% confidence interval and compared between the two arms using Fisher's exact tests.

TTD is defined as time from randomization to disease progression or death or worsening of symptoms, whichever occurs first. All primary analysis for TTD will be based on all cases receiving at least one dose of protocol treatment (i.e., all treated population). The distribution of TTD will be estimated using Kaplan-Meier method, and TTD comparisons between treatment arms will be tested primarily using log-rank test. Cox proportional-hazards models will be conducted to estimate the HR for treatment effect for TTD as a supportive analysis. Same factors included in the multivariable Cox model for PFS and baseline symptom level will be included as predictors for TTD.

Analyses pertaining to toxicity will be based on all treated cases. Adverse events will be graded using the National Cancer Institute (NCI) Common Terminology Criteria for Adverse Events (CTCAE). All treatment-emergent and baseline adverse events and hematological/biochemical toxicities based on laboratory measurements, as well as drug related AE's, will be summarized by treatment group and NCI CTCAE worst grade. The incidence of deaths and treatment-emergent serious adverse events (defined as number of patients experiencing the AE divided by all treated patients) will be summarized and compared between treatment arms using Fisher's exact test. Also, the incidence of adverse events leading to discontinuation of investigational product and/or withdrawal from the study will be summarized and listed.

In all analyses, P-values will be two-sided. A level of 0.2% will be considered statistically significant for stratified log rank test for the primary PFS analysis. For OS comparison, the significance level for stratified log rank test will be 4.8%. For all other tests, a level of 5% will be considered statistically significant.

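### Does the 4.8% level for overall survival in Section 9.4 conflict with the final boundary in Table 9.2?

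*Combined protocol and SAP*

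**What the plan says.** Section 9.1 divides a one-sided 0.025 between the two primary endpoints: "type I error rate is 0.001 for PFS test and 0.024 for OS test".

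Section 9.2.2 repeats the one-sided 2.4% for the stratified log-rank test of OS. It plans 410 deaths for 80% power at a hazard ratio of 0.75, under the interim plan of Section 9.2.3 and Table 9.2.

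Section 9.2.3 (Interim analysis for OS tests) says what the 2.4% is: "To preserve the overall one-sided type I error rate at 2.4% for the OS endpoint, critical values for rejecting null hypothesis at the interim analyses" come from a "truncated version of the Lan-DeMets spending function" of O'Brien-Fleming type. It then gives the decision rule: "If the boundary is crossed at an interim analysis or at the final analysis, then the null hypothesis will be rejected". Table 9.2 lists six interim looks and a final one. The final row shows a nominal one-sided level of 0.01872 and a boundary of 2.0808.

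The last paragraph of Section 9.4 restates the levels on the two-sided scale: "In all analyses, P-values will be two-sided". For progression-free survival (PFS): "A level of 0.2% will be considered statistically significant for stratified log rank test for the primary PFS analysis". For OS: "For OS comparison, the significance level for stratified log rank test will be 4.8" per cent. All other tests are at 5%.

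**The concern.** The OS figure in Section 9.4 stands between two numbers that are real p-value cut-offs. The PFS 0.2% is one because PFS has a single efficacy test and only futility looks before it. The 5% for other tests is one too. The OS 4.8% looks like a third cut-off, yet the paragraph neither calls it an overall level nor points to Table 9.2. An analyst who opened only Section 9.4 might compare the final OS p-value with 4.8%.

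On that reading, a final two-sided p-value between 3.74% and 4.8% would be positive under Section 9.4 and negative under Section 9.2.3. OS is a primary endpoint that may support registration, so a success threshold that could be argued after the data are seen would matter.

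**Working it through.** **Inputs.** OS level of one-sided 0.024 (Sections 9.1, 9.2.2, 9.2.3). Looks at 101, 149, 203, 261, 313, 355 and 410 deaths, with boundaries 3.3020, 3.3020, 3.2036, 2.6518, 2.4065, 2.2593 and 2.0808 (Table 9.2). Hazard ratio 0.75 and 1:1 allocation (Sections 9.2 and 9.2.2).

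**Step 1: where 4.8% comes from.** PFS: 2 × 0.001 = 0.002, the 0.2% in Section 9.4. OS: 2 × 0.024 = 0.048, the 4.8% in Section 9.4. The paragraph converts both one-sided allocations of Section 9.1 to the two-sided scale. As an overall level, 4.8% is exact.

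**Step 2: does Table 9.2 deliver that level?** The final boundary gives 1 − Φ(2.0808) = 0.0187, matching the printed 0.01872 to rounding; two-sided, 2 × 0.01872 = 3.74%. Next, the joint distribution of the seven log-rank statistics was integrated recursively, with information equal to deaths/410. The cumulative one-sided error under the null is:

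| Deaths | 101 | 149 | 203 | 261 | 313 | 355 | 410 |
|---|---|---|---|---|---|---|---|
| Cumulative error | 0.00048 | 0.00083 | 0.00130 | 0.00463 | 0.00966 | 0.01518 | 0.02391 |

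So 0.0152 is spent at the six interim looks and 0.0087 at the final one. The total of 0.0239 agrees with 2.4% at the precision of the plan. Adding 0.001 for PFS gives 0.0249, within the stated 0.025. Power, with drift ln(1/0.75) × √410 / 2 = 2.91, is 81.2%, consistent with the stated 80%.

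**Step 3: what the misreading would do.** Keep the six interim boundaries and replace only the last by z(0.024) = 1.977.

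- One-sided OS error: 0.0281, against 0.0239. With PFS added: 0.0281 + 0.001 = 0.0291, against 0.025.
- Power at a hazard ratio of 0.75: 83.4%, against 81.2%.
- Critical hazard ratio at 410 deaths, exp(−2z/√410): 0.823 at z = 1.977, against 0.814 at z = 2.0808.
- Probability of reaching the final look and landing between the two boundaries: 83.4% − 81.2% = 2.2 points at a hazard ratio of 0.75, and 0.0281 − 0.0239 = 0.0042 under the null.

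**Step 4: is 3.74% a fixed number?** No. Section 9.2.3 skips a look when information has grown by less than 10%, and lets the boundaries move with the observed deaths. As an illustration, assume an O'Brien-Fleming-type spend of 0.024 with interim boundaries capped at 3.302. The plan does not spell out the truncation; the cap is taken from the first two rows of Table 9.2. With all six interim looks this gives a final two-sided level of 3.75%, close to the printed value. With fewer interim looks, the final level at 410 deaths is:

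| Interim looks held (deaths) | Final two-sided level |
|---|---|
| 149, 261, 355 | 3.84% |
| 101, 203, 313 | 4.18% |
| 149, 261 | 4.50% |

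The gap up to 4.8% narrows as looks are skipped. A fixed final-look cut-off in Section 9.4 would therefore be wrong in many of the ways the trial could run, whereas the overall 4.8% holds in all of them.

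**The case for a change.** The best case for changing the text is that the success rule of a primary endpoint should read the same wherever it is opened. Section 9.4 is the analysis plan for that endpoint. Its OS sentence has no qualifier, and the lines on either side of it are genuine cut-offs. A final two-sided p-value of 0.04 would pass the sentence as printed and fail Table 9.2 if all six interim looks had been held. One sentence would remove the doubt, and it is better written before unblinding than after.

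The description of the wording stands: the word for an overall level is absent, there is no pointer to Table 9.2, and the neighbouring PFS figure does work as a cut-off. What does not stand is the step from there to two competing rules. Section 9.4 never says that 4.8% applies at the final look. Section 9.2.3 says how the OS null is rejected at every look, including the last, and says that otherwise superiority has not been shown. Section 9.2.2 sends the reader to that plan when it sets out the power for the same test. A specific rule with printed boundaries governs a summary line that restates its total. The misreading requires passing over those sections of the same chapter.

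**Conclusion.** No change follows. The 4.8% is the correct overall two-sided level for OS and agrees with Table 9.2, whose boundaries spend 0.0239 one-sided against an allocation of 0.024. An analyst who follows the chapter as a whole applies the Section 9.2.3 boundary at the final look and reaches a sound conclusion. The excess error of about 0.4 percentage points one-sided (0.0281 against 0.0239) arises only under a reading that the text does not state. It would affect only final observed hazard ratios between about 0.814 and 0.823, and a narrower band if interim looks are skipped.

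These figures assume proportional hazards, 1:1 allocation, 410 deaths at the final look and, except in Step 4, all six tabulated interim looks. Adding a label or a cross-reference to Section 9.4 would be a courtesy to the reader; it would alter no boundary, error rate, power figure or result.

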#### 9.5 Integrated Pharmacodynamic Biomarker Study of Acute Change in Protein Lysine Acetylation

HDAC inhibition leads to elevated protein lysine acetylation in tumor and peripheral-blood cells, which could serve as a surrogate early pharmacodynamic biomarker of entinostat activity. ENCORE 301 collected peripheral blood samples (PBMCs) for assessment of lysine acetylation, both prior to therapy and post-therapy on Days 8 and 15, using an assay developed by the [name] Laboratory, NCI/NIH. Protein lysine acetylation in the combined therapy subgroup (i.e., arm A) was associated with a striking improvement in PFS across all cell types (B cells, T cells and monocytes). In Exemestane +Entinostat-treated hyperacetylators (i.e., acetylatoin above the median) versus those with acetylation below the median, median PFS was 8.5 versus 2.7 months (HR=0.32, 95% CI 0.13, 0.79) (B cells); 6.6 versus 3.6 months (HR=0.44, 95% CI 0.18, 1.08) (T cells); and 6.2 versus 3.6 months (HR=0.50, 95% CI 0.21, 1.20) (monocytes).

We will use the identical methodology, central laboratory ([name] Laboratory, NCI/NIH), and timing (Day 15) for the integrated acetylation pharmacodynamic

Rev. 9/17

biomarker studies planned in E2112. PBMCs will be collected at baseline and 15 days after initiating therapy consisting of drawing 8cc of blood into one blue/black CPT citrate tube at each time point.

Since exemestane is not expected to induce significant increase in protein lysine acetylation, we expect no significant increase in protein lysine acetylation after two weeks of arm B treatment on E2112. The primary test of association between increased protein lysine acetylation (as an early pharmacodynamic biomarker of entinostat activity) and PFS will be examined in arm A in E2112. However, since the study is blinded, the PBMCs will be collected on all patients (including both arm A and arm B). The prognostic value of increase of lysine acetylation will be conducted in arm B as well as an exploratory analysis. All 600 patients enrolled in the main trial will be included in the integrated acetylation pharmacodynamic biomarker study. The analysis will be performed at about 70 months after study activation (same time as that for final OS analysis).

#### 9.5.1 Statistical consideration for integrated acetylation pharmacodynamic biomarker study

The objective of this pharmacodynamic biomarker study is to examine the prognostic value of acute acetylation change for PFS in patients receiving Exemestane + Entinostat combination therapy. We hypothesize that patients with percentage change in protein lysine acetylation above median will have a prolonged PFS compared to those with changes in protein lysine acetylation below or equal to median in arm A. For this integrated pharmacodynamic biomarker study, the endpoint is PFS. The group variable is change in protein lysine acetylation between baseline and 2 weeks after initiating therapy.

Of the 300 refractory patients on arm A, 270 (90%) of them will be expected to have measures for protein lysine acetylation at both baseline and 2 weeks after initiating therapy. The percentage change in lysine acetylation will be calculated for all patients on arm A and the median percentage change will be determined and used as the threshold to dichotomize all patients into two groups on the arm:  $>$  median and  $\leq$  median. There will be about 266 PFS events on arm A at the time of the analysis (70 months after study activation) under the alternative hypothesis. With a total of 266 PFS events and 270 patients, there will be adequate power (80%) to detect a hazard ratio of 0.71 and excellent power (90%) to detect a hazard ratio of 0.67 using log rank test with one-sided type I error equal to 2.5%.

#### 9.5.2 Analysis plan for integrated acetylation pharmacodynamic biomarker study

The primary analyses for this integrated acetylation pharmacodynamic biomarker study will be conducted in all patients on arm A who have data about the protein lysine acetylation at both baseline and 2 weeks after initiating therapy. The analysis time for this acetylation biomarker study is at about 70 months after study activation (same time as final analysis for OS).

The distributions of PFS and OS will be estimated using the Kaplan-Meier method, with 95% confidence intervals calculated using

Greenwood's formula. Differences between patients with above or below median of percentage change in protein lysine acetylation will be tested using log rank test. Univariate and multivariable Cox models will be built to estimate the HRs for the effect of increased protein lysine acetylation for PFS and OS, respectively. The adjusting variables in the multivariable Cox model include patient demographics and disease characteristics, such as age at diagnosis, ECOG PS, disease stage, prior therapy, et al.

Similar analysis will be conducted in patients on arm B to explore whether increase of protein lysine acetylation is prognostic for PFS and OS in patients with the exemestane monotherapy.

In all the above survival analyses, landmark method will be used, with landmark set at 2 weeks. OS is defined to be week 2 to death from any cause, censoring cases who are alive at the date last known alive. PFS is defined to be week 2 to the earliest of documented disease progression as defined by the RECIST criteria, new primary breast cancer, or death without progression. Cases with incomplete follow up or without adequate disease evaluations will be censored at the date last documented to be free of progression. Patients who have events for OS or PFS within 2 weeks are excluded from the landmark analysis.

The distribution of the percentage change in protein lysine acetylation will be plotted for the two treatment groups and difference will be compared using the Wilcoxon ranks sum test. Tumor response rate will be compared between the patients with percentage change in acetylation being above or below median using Fisher's exact tests in each treatment arm.

All above analyses for protein lysine acetylation change will be repeated for all three types of peripheral blood mononuclear cells (CD3+ T cells, CD19+ B cells and CD14+ monocytes). In all analyses, P-values will be two-sided and a level of 5% will be considered statistically significant. No adjustment will be made for multiple comparisons.

If PFS endpoint is positive in the primary analysis within the first 360 patients, the acetylation data will be analyzed for a subgroup analysis for PFS (all 360 patients will be dichotomized into one of two groups based on the whole sample median: > median and ≤ median) at the PFS primary analysis time.

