The ENCORE 301 randomized phase 2 study evaluated the role of entinostat, a class 1 selective HDAC inhibitor, in combination with exemestane (steroidal AI) in the advanced breast cancer setting. Postmenopausal women who had received  $\leq 1$  prior chemotherapy and were progressing on a non-steroidal AI were randomized to exemestane 25 mg daily plus entinostat 5 mg weekly versus exemestane plus placebo weekly. A significant improvement in PFS was noted in the entinostat arm versus placebo (median 4.3 versus 2.3 months, respectively). In an exploratory analysis of patients who were deemed resistant to prior AI, patients randomized to the entinostat arm had a greater PFS than those in the placebo arm. OS, an exploratory endpoint, was also significantly longer in the entinostat arm versus the placebo arm (28.1 versus 19.8 months, respectively). Interestingly, in a subset analysis examining protein acetylation in entinostat patients (n=27), the median PFS increased to 8.5 months in those exhibiting protein lysine hyperacetylation, and this was apparent after just 2 weeks of therapy. The addition of entinostat to AI therapy may delay the initiation of subsequent therapies such as chemotherapy by prolonging PFS on exemestane. We propose to evaluate the addition of entinostat or placebo to exemestane in patients who have progressed on a non-steroidal AI. In addition, we will explore whether benefit varies with changes in lysine acetylation.

Rev.10/15 **Table 1.1: Select Clinical Trials of Novel Combinations with Endocrine Therapy in Metastatic Breast Cancer**

Clinical Trial	Treatment Arms	Patient Population	Results
ENCORE Phase 2 Trial 	Exemestane + Entinostat/Placebo 5mg po weekly	Postmenopausal women Prior progression on a non-steroidal AI and $\leq 1$ prior chemotherapy	Median PFS 4.3 (entinostat) versus 2.3 months (placebo); HR 0.73 Median OS 28.1 (entinostat) versus 19.8 months (placebo); HR 0.59
Rev. 4/15 ECOG-ACRIN Phase 3 Trial ([name])	Exemestane + Entinostat/Placebo 5 mg po weekly	Pre/perimenopausal and post-menopausal women and men HR-positive advanced breast cancer Prior progression on a non-steroidal AI (adjuvant/metastatic) and $\leq 1$ prior chemotherapy for metastatic disease	Pending
BOLERO-2 Phase 3 Trial 	Exemestane + Everolimus/Placebo	Postmenopausal women Prior progression on a non-steroidal AI and $\leq 1$ prior chemotherapy	Median PFS 7.8 (everolimus) vs 3.2 (placebo) months

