### 2.2 Secondary Objectives

- 2.2.1 To evaluate the safety and tolerability of entinostat in combination with exemestane, and to compare the safety profile to that of endocrine therapy with placebo.
- 2.2.2 To evaluate the objective response rate of exemestane in combination with entinostat or placebo.
- 2.2.3 To evaluate whether the efficacy of exemestane with entinostat varies with changes in acetylation status in peripheral blood mononuclear cells (PBMCs).
- 2.2.4 To evaluate the time to treatment deterioration (as defined by decrease in HRQL, progression, death) of exemestane + entinostat versus exemestane + placebo arms.
- 2.2.5 To evaluate the differences in overall health-related quality of life (HRQL) between the exemestane + entinostat versus exemestane + placebo arms.
- 2.2.6 To evaluate the difference with respect to specific symptoms that are associated with entinostat, i.e., fatigue, nausea, anorexia and diarrhea, between the exemestane + entinostat versus exemestane + placebo arms.
- 2.2.7 To measure adherence to protocol therapy.
- 2.2.8 To evaluate the pharmacokinetics of entinostat in patients with advanced breast cancer.
- 2.2.9 To evaluate what, if any, patient variables alter the pharmacokinetic profile of entinostat in patients with advanced breast cancer.

Rev.10/16

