### 12.1 Acute Change in Protein Lysine Acetylation as a Predictor of Benefit from Entinostat

This analysis will be performed in the laboratory of [name] at NCI/NIH (See Section 12.2). Protein lysine acetylation will be measured by multiparameter flow cytometry in peripheral blood mononuclear cells (PBMCs; CD19+ B cells, CD3+ T cells, and CD14+ monocytes). [name] and her team have developed and published the method to be utilized to perform this correlative analysis, which includes determination of the stability of acetylation in PBMC samples. In addition the team has been coauthors on four clinical trials, including ENCORE 301, in which the flow cytometric pharmacodynamic assay has been performed.

Peripheral blood mononuclear cells (PBMCs) offer an opportunity to assess pharmacodynamic effects of entinostat and to correlate the observed effects with breast cancer outcome. In PBMCs, the effects of entinostat will be measured by global protein acetylation using multi-parameter flow cytometry.

We hypothesize that patients with increased protein lysine acetylation in the two weeks after initiating therapy will have a prolonged PFS compared to those without changes in protein lysine acetylation.

To briefly review, ENCORE 301 collected PBMCs for assessment of lysine acetylation prior to therapy, and post-therapy on Days 8 and 15 using an assay developed by the [name] Laboratory, NCI/NIH. Protein lysine acetylation in the combined therapy subgroup was associated with a striking improvement in PFS across all cell types. In EE-treated hyperacetylators versus those with acetylation below the median, median PFS was 8.5 versus 2.7 months (HR=0.32, 95% CI 0.13, 0.79) (B cells); 6.6 versus 3.6 months (HR=0.44, 95% CI 0.18, 1.08) (T cells); and 6.2 versus 3.6 months (HR=0.50, 95% CI 0.21, 1.20) (monocytes).

We will use the identical methodology, central laboratory ([name] Laboratory, NCI/NIH), and timing (Day 15) for the acetylation studies planned in E2112. While our data will not independently contribute to the validation effort, it will further expand the pharmacodynamic data and add measurably to our interpretation of the clinical data.

Rev.10/16

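### The acetylation objective asks whether benefit from entinostat varies with acetylation change, but the only powered test, within arm A, measures prognostic association and cannot show differential benefit

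*Combined protocol and SAP*

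**What the plan says.** Three places set a question about differential benefit. Objective 2.2.3 is "To evaluate whether the efficacy of exemestane with entinostat varies with changes in acetylation status in peripheral blood mononuclear cells (PBMCs"). Section 1.3.4 says "we will explore whether benefit varies with changes in lysine acetylation". Section 12.1 is headed "Acute Change in Protein Lysine Acetylation as a Predictor of Benefit from Entinostat".

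Section 9.5.1 sets a different one: "The objective of this pharmacodynamic biomarker study is to examine the prognostic value of acute acetylation change for PFS", in patients on the combination. The analysis follows section 9.5.1. Section 9.5 places the primary test of association in arm A, and section 9.5.2 says the primary analyses "will be conducted in all patients on arm A who have data about the protein lysine acetylation at both baseline and 2 weeks". Patients are split at the median percentage change, PFS is landmarked at 2 weeks, and "Differences between patients with above or below median of percentage change in protein lysine acetylation will be tested using log rank test". No stratification is mentioned. Multivariable Cox models are also planned, with an open list of covariates that does not name baseline acetylation.

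Two further analyses touch the question. Arm B gets a similar, exploratory analysis of whether the marker is prognostic on exemestane alone. If PFS is positive in the first 360 patients, they are divided at the whole-sample median for a subgroup analysis of PFS. Neither description names an interaction test or any other formal comparison of the marker effect between arms. Section 9.6.2, by contrast, separates the prognostic from the predictive value of QOL and assigns the latter to a QOL-by-treatment interaction test.

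**The concern.** Whether benefit varies with a marker is a question about the treatment effect, entinostat against placebo, at different marker levels. A comparison of two non-randomized groups who all received entinostat holds no information on that effect. High changers may do better because entinostat helps them more, or because a larger acetylation change goes with a better outlook on any treatment. The arm A test rejects in both cases and cannot tell them apart.

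At stake is what the trial may conclude. A positive arm A result could be taken, under objective 2.2.3 and the 12.1 heading, as evidence that acetylation change identifies who benefits. The PFS and OS conclusions are not affected.

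**Working it through.** **Inputs.** From section 9.5.1: 270 arm A patients with both samples, 266 PFS events, a median split (1:1), one-sided 2.5%. Section 9.5.2 uses two-sided 5%, which has the same critical value, 1.96. From section 9.2.1: median PFS 4.1 months (arm B) and 7.1 months (arm A), treatment HR 0.58. The documents give no prognostic hazard ratio for the marker, so a range is assumed.

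**1. The plan's own figures.** With exponential PFS, 40 months of uniform accrual and a cut at 70 months, expected events are n × [1 − (e^(−30λ) − e^(−70λ)) / (40λ)]. With λ = ln 2 / 7.1 and n = 270 this gives 266.4, matching the stated 266.

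Power of the log-rank test is Φ(|ln HR| × √266 / 2 − 1.96), with √266 / 2 = 8.155.
- HR 0.71: 0.3425 × 8.155 = 2.793; Φ(0.833) = 79.8%. Stated: 80%.
- HR 0.67: 0.4005 × 8.155 = 3.266; Φ(1.306) = 90.4%. Stated: 90%.

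The stated power is correct for the within-arm comparison.

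**2. The same test when the marker is only prognostic.** Suppose high against low change has the same hazard ratio in both arms. There is then no effect modification, and the formula in step 1 gives the probability of rejecting:

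| Prognostic HR (assumed) | Arm A test rejects |
|---|---|
| 0.90 | 13.5% |
| 0.85 | 26% |
| 0.80 | 44% |
| 0.71 | 80% |
| 0.67 | 90% |

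**3. Dependence on the drug effect.** Simulation, 4,000 runs per scenario, 270 marker patients per arm, exponential PFS, cut at 70 months:

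| Prognostic HR | Entinostat HR | Arm A test rejects | Between-arm contrast rejects |
|---|---|---|---|
| 1.00 | 1.00 | 2.4% | 2.3% |
| 1.00 | 0.58 | 2.5% | 2.3% |
| 0.71 | 1.00 (helps nobody) | 80.4% | 2.2% |
| 0.71 | 0.58 (helps all equally) | 79.0% | 2.5% |
| 0.67 | 1.00 | 89.8% | 2.6% |
| 0.67 | 0.58 | 91.0% | 2.7% |

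The first two rows show that the test holds its level for the association null. When the marker is not prognostic but does modify the effect (ratio of hazard ratios 0.71), the arm A test rejects in 79.2% of runs, about the same as for a purely prognostic marker of 0.71.

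**4. What a between-arm contrast could do.** Assume 270 marker patients in arm B as well, with about 270 events (the step 1 formula with median 4.1 gives 269.7). The variance of the difference in log hazard ratios is 4/266 + 4/270 = 0.02985, a standard error of 0.1728. Power at a ratio of 0.71 is Φ(0.3425 / 0.1728 − 1.96) = 51%, and at 0.67 it is 64%. For 80% power the detectable ratio is e^(−2.802 × 0.1728) = 0.62. Reaching 80% at 0.71 needs 16 × 2.802² / 0.3425² ≈ 1,070 events, against 266 + 270 = 536.

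**5. Confounding by another factor.** Take an assumed risk factor of 50% prevalence, PFS HR 1.5 to 2.0, and correlation phi 0.1 to 0.3 with the marker group. The crude marker log HR is then about phi × ln HR.
- If the factor is commoner in low changers: from 0.1 × ln 1.5 × 8.155 = 0.33, Φ(−1.63) = 5%, to 0.3 × ln 2 × 8.155 = 1.70, Φ(−0.26) = 40%. Simulation gives 5% to 34%; the crude formula overstates the upper end.
- If it is commoner in high changers: Φ(−2.29) = 1% down to Φ(−3.66), below 0.1%. Simulation gives 0 to 1%.

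The fair range is roughly 0% to 35% around the nominal 2.5%, with nothing in the documents to fix the sign. Stratifying on the confounder itself restores 2.4% to 2.9%. Stratifying on factors unrelated to it still leaves 6% to 29% in the unfavourable direction.

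**The case against.** The strongest reply is that the test matches its own hypothesis. Section 9.5.1 announces a prognostic objective in treated patients, and the one-sided 2.5% is claimed for that test alone. This stands. A reader might infer that the stated error rate is wrong; it is not, as step 3 shows. What remains is that 2.2.3, 1.3.4 and the 12.1 heading promise more than this test can give. The phrase about the efficacy of the combination in 2.2.3 could be read as outcome on the combination, but 1.3.4 and the 12.1 heading speak of benefit.

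A reader might also infer that the result will be reported as predictive of benefit. The documents do not say so. The body of section 12.1 states a PFS hypothesis and says these data will not independently contribute to validation. The risk comes from the headline wording, not from a declared reporting rule.

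Nor is the plan silent on related analyses. The Cox models adjust for several factors, and their open list does not exclude baseline acetylation. The arm B repeat could reveal a marker that tracks PFS without entinostat. No rule says that significance in A without significance in B will count as evidence. Such a reading would be unsound: for a marker equally prognostic at HR 0.71 it occurs with probability about 0.80 × 0.20 = 16%. The conditional subgroup analysis does include both arms. But it depends on a positive PFS result and names no interaction test. Since section 9.5 expects no significant rise in arm B, a pooled median would largely sort patients by arm.

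Finally, a reader might infer that confounding inflates the error, or that stratification cures the problem. Neither follows: the shift can go either way, and stratification on other factors leaves a truly prognostic marker just as prognostic.

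**Conclusion.** The concern holds as a mismatch between the stated question and the only powered analysis. The arm A test is valid for prognostic association and uninformative about differential benefit. For a purely prognostic marker it rejects about 14%, 44% and 80% of the time at assumed hazard ratios of 0.90, 0.80 and 0.71, whatever the drug effect. These figures rest on exponential PFS, 266 events, and an assumed equal prognostic hazard ratio in both arms. The confounding range of roughly 0% to 35% rests on assumed strengths and is secondary. The stated power figures are not in error. This is a secondary objective, but the correction changes what the trial may claim.

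**What to change.** 1. Reword objective 2.2.3, the sentence in 1.3.4 and the 12.1 heading as *association of acetylation change with PFS among patients treated with entinostat*, in line with section 9.5.1.
2. Add to section 9.5.2 that the arm A result, alone or set informally beside arm B, will not be read as evidence that benefit from entinostat varies with acetylation.
3. As a secondary improvement, stratify the arm A log-rank and Cox analyses on the four randomization factors, and name baseline acetylation in the multivariable Cox model already planned. Percentage change has the baseline value in its denominator, so the two are linked. This reduces confounding by those measured factors only and does not turn the test into one of differential benefit.

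An interaction test is not a clean substitute. The marker is measured after treatment starts, arm-specific medians would define different groups, and power would be only 51% at a ratio of 0.71.

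The cost is protocol and SAP wording, using data already planned for collection. The permitted claim is narrower, and the adjusted analysis may lose a little power where covariates share information with the marker.
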